## 1 LIST OF ABBREVIATIONS AND DEFINITIONS OF TERMS

---

Abbreviation or Term	Definition
AE	Adverse event
Alpha	Distribution rate constant
ANOVA	Analysis of variance
AUC	Area under the plasma concentration-time curve
AUC inf	AUC from zero to infinity
AUC t	AUC from time zero to the time of the last measurable concentration
%AUC extrap	Percent of AUC extrapolated to infinity
Beta	Elimination rate constant
BLQ	Below limit of quantitation
BMI	body mass index
BP	Blood pressure
CGI-I	Clinical Global Impression – Improvement Scale
CI	Confidence interval
C max	Maximum observed plasma concentration
CL/F	Apparent oral clearance
CV	Coefficient of variation
DM1	Myotonic dystrophy type 1
ECG	Electrocardiogram
EEG	Electroencephalograph
EDS	Excessive daytime sleepiness
ESS	Epworth sleepiness scale
GCP	Good clinical practice
K 10	Elimination rate constant
K 21	Intercompartmental distribution rate constant
MedDRA	Medical Dictionary for Regulatory Activities
n, N	number
PGI-I	Patient Global Impression – Improvement Scale
PK	pharmacokinetic(s)
PVT	Psychomotor Vigilance Task
SAE	Serious adverse event
SD	Standard deviation
SOC	System organ class
SSS	Stanford Sleepiness Scale

---

Abbreviation or Term	Definition
-----------------------------	-------------------

---

TEAE(s)	Treatment-emergent adverse events
$t_{1/2}$	Terminal elimination half-life
$T_{max}$	Time of maximum observed plasma concentration
V	Volume of distribution
V1	Volume of central compartment
$\lambda_z$	Terminal elimination rate constant

## 2 STUDY OVERVIEW

This is a multi-center, randomized, double-blind, placebo-controlled, two-treatment crossover study in participants with DM1.

In this study participants who have consented and meet all-eligibility criteria will receive two treatments, IV Placebo (Treatment A) and ERX-963 (Treatment B or C) in a crossover fashion with approximately 4 to 18 days washout between the treatments (Note: washout days are counted from the day of dosing in Period 1). The study will be conducted in two cohorts.

In cohort 1, approximately six (6) participants will be randomized to one of two sequences:

- Sequence 1: Treatment A: IV Placebo in Period 1 →  
4 to 18 days washout →  
Treatment B: 1 mg ERX-963 in Period 2
- Sequence 2: Treatment B: 1 mg ERX-963 in Period 1 →  
4 to 18 days washout →  
Treatment A: IV Placebo in Period 2

ERX-963 1 mg or placebo will be administered intravenously over 5 minutes.

In cohort 2, approximately six (6) participants will be randomized to one of two sequences:

- Sequence 1: Treatment A: IV Placebo in Period 1 →  
4 to 18 days washout →  
Treatment C: Selected ERX-963 dose in Period 2
- Sequence 2: Treatment C: Selected ERX-963 dose in Period 1 →  
4 to 18 days washout →  
Treatment A: IV Placebo in Period 2

The selected ERX-963 dose (0.5 mg, 1 mg or 2 mg) or placebo will be administered intravenously over 5 minutes (0.5 mg or 1 mg) or 15 minutes (2 mg).

ERX-963 dose for cohort 2 will be selected based on a *blinded review* of safety data from cohort 1. A decision to proceed to cohort 2 with the planned 2 mg dose, to lower the dose to 1 mg or 0.5 mg, or cease dosing altogether, will be made jointly by the medical monitor and the principal investigators and will be based on the clinical nature of adverse events, safety laboratory and vital signs abnormalities observed during cohort 1.

Blinding of placebo and investigational drug will be maintained during randomization, drug administration, and complete assessment periods for each cohort.

### 3 STUDY OBJECTIVES

#### Primary

The primary objectives of the study are to assess the safety and tolerability of a single dose of ERX-963 versus placebo in patients with Myotonic Dystrophy Type 1 (DM1).

#### Secondary

The secondary objectives for the study are to assess the effect of intravenously administered ERX-963 versus placebo on sleepiness, vigilance, and working memory in patients with DM1.

#### Exploratory

There are two exploratory objectives for this study:

- To correlate ERX-963 plasma concentrations to clinical efficacy endpoints in patients with DM1
- To assess the effect of intravenously administered ERX-963 versus placebo on brain activity in patients with DM1.

### 4 GENERAL METHODS

#### 4.1 Analysis Populations

**Screened Population:** The screened population will be defined as all patients who sign the informed consent documents.

**Safety Population:** The safety population will be defined as all patients who sign the study-specific informed consent documents and receive at least 1 dose of study medication. Participants will be analyzed according to the intervention they received.

**Evaluable Population:** All treated patients who complete all the protocol specified assessments in both treatment periods.

**Enrolled Population:** All participants who receive at least one dose of study intervention.

**PK Population:** The PK Population will include all patients who receive the dose of ERX-963 study drug, have no major protocol deviation that may impact PK, and have enough postbaseline concentration data to obtain at least one reliable estimate of a key PK parameter.

#### 4.2 Summarization of Data

Study results will be summarized by treatment group [for example., A, B, or C] or by treatment sequence [for example, A-B, B-A, A-C, C-A] unless otherwise specified.

No imputation of missing data will be performed. No windowing of visits will be performed unless otherwise specified.

### **4.3 Sample Size Justification**

No formal sample size calculations were performed.

Approximately 20 participants will be screened and at least 6 evaluable participants per cohort are expected to complete the study.

Participants who do not complete the crossover portion of the study will be discontinued and replaced with a new participant.

### **4.4 Randomization**

On the day of dosing in Period 1 participants will be assigned a unique number (randomization number) in ascending numerical order at each study site. The randomization number encodes the participant's assignment to one of the two treatment sequences of the study [Sequence 1: AB and Sequence 2: BA in Cohort 1; Sequence 1: AC and Sequence 2: CA in Cohort 2], according to the randomization schedule generated prior to the study. Each participant will be administered blinded study intervention, labeled with his/her unique randomization number, throughout the study.

### **4.5 Output Production and Validation**

All analyses will be performed using SAS V 9.3 or higher (SAS Institute, Inc, Cary, North Carolina, USA). Validation and quality control of the tables and listings, which display the results of the statistical analysis of the data from this study, will follow the appropriate Innovative Analytics standard operating procedures (SOPs).

## **5 SUBJECT DISPOSITION**

The number of patients who are screened, who receive at least one dose of study intervention, completed the study or who discontinue, and the reasons for discontinuation from the study will be summarized in tabular format for the safety population. All disposition data will be displayed for all patients in the safety population in a subject listing. An additional listing will be provided with information on patients who were screened but did not receive study treatment.

## **6 DEMOGRAPHIC CHARACTERISTICS**

For quantitative variables (e.g., age, height, weight, and body mass index [BMI]), summary statistics (number [n], mean, standard deviation [SD], minimum, median, and maximum) will be presented for the safety population. For the qualitative variables (e.g., sex, race, and ethnicity), results will be summarized as counts and percentages for the safety population. Individual demographic information for the safety population will be displayed in subject listings.

## **7 MEDICAL HISTORY**

The number and percent of patients with past and current medical disorders at Screening will be presented by SOC and preferred term. All findings will be displayed for the safety population in a subject listing.

## **8 DM1 DIAGNOSIS HISTORY**

Variables collected in the DM1 Diagnosis History will be summarized as counts and percentages for the safety population. The only 2 exceptions will be the age of DM1 diagnosis, age of onset of symptoms and time since onset of excessive sleepiness or hypersomnia which will analyzed with summary statistics (number [n], mean, standard deviation [SD], minimum, median, and maximum). All history findings will be displayed for the safety population in a subject listing.

## **9 MDHI AND EPWORTH SLEEPINESS SCALE**

Variables collected in the MDHI and Epworth Sleepiness Scale will be summarized as counts and percentages for the safety population. Both scales will be displayed for the safety population in subject listings.

## **10 PHYSICAL EXAM**

A full physical exam is collected at Screening and brief physical exams are conducted once during Period 1, Period 2 and at the End of Study visit/Early Discontinuation. Any clinically significant findings are to be recorded on the Medical History Form or the Adverse Event forms. Abnormal findings which are not clinically significant are captured on the Physical Exam CRF. Therefore, there will be no summaries of physical exam findings or changes in physical exam findings. All Physical Exam data will be provided in patient listings.

## **11 PRIOR AND CONCOMITANT MEDICATIONS**

The prior medications and concomitant medications will be coded by the Anatomical Therapeutic Chemical (ATC) Class and Preferred name using the World Health Organization Drug (WHODrug) Dictionary (Enhanced), March 2019 version.

Summaries will be done for concomitant medication and will present the number and percentage of patients who use each medication by cohort. Patients who report more than one medication within the same ATC class or within the same preferred name within the same category (e.g., concomitant medications) will be counted only once within each level. The summary table will include all medications from the time of the first dose of study drug until the End of Study visit.

Medications other than the study drug will be classified based on start date and end date relative to the date of the first dose of study drug. The categories of prior medications and concomitant medications are defined as the following:

- A 'prior medication' is any medication started and stopped prior to date of the first dose of study drug

- A ‘concomitant medication’ is any medication started on or after the date of first dose of study drug or any medication which started prior to the date of first dose of study drug and is ongoing at the time of dosing. In addition, only those medications which have started prior to the End of Study visit will be included.

The patient listing will include all medications.

## **12 SAFETY ANALYSES**

### **12.1 Adverse Events**

Adverse events will be coded using the Medical Dictionary for Regulatory Activities (MedDRA) coding system (using the MedDRA Version stated in Data Management Plan). An overall summary table will be presented by treatment group that summarizes all treatment-emergent adverse events (TEAEs), all serious TEAEs, all drug-related TEAEs, number of deaths, and all severe TEAEs for the safety population. In addition, frequency tables will be presented by treatment group for all TEAEs, for all drug related adverse events, and for all adverse events resulting in discontinuation from study, by system organ class and preferred term for the safety population. The frequency tables will be ordered by system organ class. Subject listings of all TEAEs, serious TEAEs, and drug related TEAE will also be provided.

In all displays, TEAEs will be displayed by MedDRA System Organ Class and Preferred Terms, with patients who have the same TEAE counted only once for that event and with patients who have more than one TEAE within a System Organ Class counted only once in that System Organ Class.

Pretreatment adverse events are defined as those events which occur between time of signing the informed consent and the first dose of study medication. Pretreatment AEs will be listed separately from the TEAEs.

Treatment-emergent AEs will include AEs which start between the date and time of study drug dosing and through Study Day 2, within each period.

All TEAEs will be listed by treatment sequence, subject, and timing of event. Treatment taken just prior to the event will be provided in the listing.

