### 6.1. Study Intervention(s) Administered

Treatment Name	ERX-963	Placebo
Intervention Name	██████████	Normal saline (0.9% Sodium Chloride)
Type	Drug	Placebo
Dose Formulation	Intravenous	Intravenous
Unit Dose Strength(s)	0.1 mg/ml ██████████	Not Applicable
Dosage Level(s)	
Cohort 1 Single IV Administration 1 mg over 5 minutes
 
Cohort 2 Single IV Administration 0.5 mg or 1 mg over 5 minutes or 2 mg over 15 minutes
	
Single IV Administration over 5 minutes
 
Single IV Administration over 5 minutes or 15 minutes

Route of Administration	IV infusion	IV infusion
Investigational Medical Product (IMP) and Non-IMP	██████████ (IMP)	Normal Saline (NIMP)
Sourcing	Each site will source the drug product, IV ██████████ through their pharmacy.	Each site will source the placebo, normal saline, through their pharmacy.
Packaging and Labeling	Not Applicable	Not Applicable

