### 6.2. Preparation/Handling/Storage/Accountability

ERX-963 (IV ██████████) will be procured by the pharmacy at the clinical sites. IV ██████████ is available as 5 mL or 10 mL vial, containing 0.1 mg/mL of drug. Appropriate volumes for each dose level as summarized in the Table below will be administered over the duration specified.

Dose	Total Volume	Dosing Plan
0.5 mg	5 mL	ERX-963 0.5 mg or placebo will be administered intravenously over 5 minutes.
1.0 mg	10 mL	ERX-963 1 mg or placebo will be administered intravenously over 5 minutes.
2.0 mg	20 mL	ERX-963 2 mg or placebo will be administered intravenously over 15 minutes.

1. The investigator or designee must confirm appropriate temperature conditions have been maintained during transit for all study intervention received and any discrepancies are reported and resolved before use of the study intervention.  
IV ██████ vial should be stored at 25 ° C (77 ° F); excursions permitted to 15 ° to 30 ° C (59 to 86 ° F).
2. Only participants enrolled in the study may receive study intervention and only authorized site staff may supply or administer study intervention. All study intervention must be stored in a secure, environmentally controlled, and monitored (manual or automated) area in accordance with the labeled storage conditions with access limited to the investigator and authorized site staff.
3. The investigator, institution, or the head of the medical institution (where applicable) is responsible for study intervention accountability, reconciliation, and record maintenance (ie, receipt, reconciliation, and final disposition records).
4. Further guidance and information for the final disposition of unused study interventions are provided in the Pharmacy Manual.

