#### 9.4.2. Safety Analyses

All safety analyses will be performed on the Safety Population.

Endpoint	Statistical Analysis Methods
Primary	Proportion of patients experiencing AEs, SAEs, drug-related AEs, adverse events resulting in discontinuation, by treatment and cohort
Exploratory	Will be described in the statistical analysis plan finalized before database lock

Safety and tolerability are assessed by tabulation of the frequency per participant of adverse events, drug-related adverse event, adverse events that cause discontinuation, and serious adverse events. Tabulation will be by primary term and system organ classification (SOC), cohort and treatment.

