## 14.2 Psychomotor Vigilance Task (PVT)

For PVT, three variables will be analyzed: the number of attentional lapses, the reciprocal of the longest 10% response time of each trial, and the median reaction time.

Cohort 1 and Cohort 2 data will be combined. Treatments will be analyzed such that there are 4 treatment groups: Placebo in Cohort 1, 1 mg ERX-963, Placebo in Cohort 2, and Selected ERX-963.

A mixed effects model will be used to compare efficacy effects following ERX-963 versus placebo. The change from baseline for each of the three PVT variables will be used in the model as the dependent variable. The model will include cohort, sequence, cohort-by-sequence interaction, treatment, treatment period, predose baseline, measurement time point, measurement time-by-baseline interaction, and measurement time-by-treatment interaction as fixed effects, with subject (within cohort and sequence) as random effect. The test statistic will be based on the treatment effects (experimental versus placebo, averaged across the post-dose measurements), using the equally weighted mean of the Cohort 1 and Cohort 2 treatment effects.

The SAS code will be as follows:

```
Proc mixed data = xxxx;
Class patnum cohort sequence period treatment timept;
Model cfb_effvariable = cohort sequence cohort*sequence treatment period
      baseline timept timept*baseline timept*treatment;
Random patnum(cohort sequence) / subject = patnum(cohort sequence);
Estimate 'ERXvPBO' treatment 0.5 -0.5 0.5 -0.5;
Estimate 'ERXvPBOC1' treatment 1 -1 0 0;
Estimate 'ERXvPBOC2' treatment 0 0 1 -1;
Run;
```

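### Does the SAP drop the cohort split that the protocol asks for in the primary adverse event tables?

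*SAP*

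**What the plan says.** The protocol names cohort twice for the primary endpoint. The endpoint row of Protocol 9.4.2 reads "Proportion of patients experiencing AEs, SAEs, drug-related AEs, adverse events resulting in discontinuation, by treatment and cohort", and the text beneath it adds "Tabulation will be by primary term and system organ classification (SOC), cohort and treatment".

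SAP 12.1 gives the grouping as treatment group only, both for the overall summary table and for the frequency tables: "frequency tables will be presented by treatment group for all TEAEs, for all drug related adverse events". The general rule in SAP 4.2 is "Study results will be summarized by treatment group [for example., A, B, or C] or by treatment sequence", and it leaves room for other specifications.

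Treatment A is placebo in both cohorts, B is 1 mg in Cohort 1, and C belongs to Cohort 2 (SAP 2: "Treatment C: Selected ERX-963 dose in Period 2"). For the PVT, SAP 14.2 combines the cohorts and lists four groups: "Placebo in Cohort 1, 1 mg ERX-963, Placebo in Cohort 2, and Selected ERX-963". SAP 14.3 does the same for the SSS.

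**The concern.** Read on its own, SAP 12.1 together with the A, B or C examples in SAP 4.2 suggests three columns with a single placebo column. That is not the display the protocol describes, it concerns the primary endpoint, and the SAP records no departure from the protocol.

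Two features make the reading uncomfortable. The cohorts are dosed one after the other. The placebo infusion may also differ between them: it takes 5 minutes in Cohort 1, while the Cohort 2 entry in Protocol 6.1 is "Single IV Administration over 5 minutes or 15 minutes", and Protocol 6.2 ties the longer time to the highest dose ("ERX-963 2 mg or placebo will be administered intravenously over 15 minutes"). If placebo AE rates differed by cohort, a combined column would show each dose beside an average to which the other cohort contributes about half.

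**Working it through.** **Which columns are in doubt.** Treatments B and C are each given in one cohort only, so coding by treatment already separates active treatment by cohort. This holds even if Cohort 2 receives 1 mg, because the codes stay distinct. Only Treatment A spans both cohorts. The protocol's grouping gives four columns and the literal A, B, C grouping gives three; the difference is one split of placebo.

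**What the SAP means by treatment elsewhere.**

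- SAP 14.2 and 14.3 state four groups, with placebo split by cohort.
- SAP 14.5 (CGI-I and PGI-I) does not list the groups, yet its code uses the contrast 0.5, -0.5, 0.5, -0.5, which needs a four-level treatment variable. The SAP therefore uses the four-level coding without always spelling it out.
- SAP 14.4 (One-back) has two groups within each cohort, analysed separately, so placebo is not pooled there either.
- SAP 4.2 offers A, B or C as examples, not as a definition.

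**Whether table titles decide it.** They do not. In the SAP mockup contents the AE tables are titled by treatment, but so are the PVT and SSS inferential tables, whose models have four groups. Concomitant medications are by cohort in SAP 11 and by treatment in the title of Table 14.1.8. The columns are fixed by the shells (SAP Mockups, Version 1.0, cited in the April 2020 memo), which are not in the available text.

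**Whether the breakdown is lost.** It is not. SAP 12.1 lists treatment-emergent events by sequence, subject and timing, with the treatment taken just before each event. SAP 4.4 assigns AB and BA to Cohort 1 and AC and CA to Cohort 2, so sequence identifies cohort. Dosing records are also listed by patient, which gives the denominators.

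**Precision under each layout.** The documents give no AE rates and no planned precision, so there is no figure to reproduce. SAP 4.3 expects at least 6 evaluable participants per cohort; take exactly 6. With no events in n participants, the upper limit of the exact two-sided 95% interval is 1 - 0.025^(1/n):

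| Placebo column | n | Upper limit for 0 events |
|---|---|---|
| One cohort | 6 | 1 - 0.025^(1/6) = 45.9% |
| Both cohorts | 12 | 1 - 0.025^(1/12) = 26.5% |

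**How often split columns would differ by chance.** For two independent Binomial(6, p) counts with the same p, the probability that they differ is 1 minus the sum over k of P(X = k) squared. With assumed values of p:

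| p | P(counts differ by at least 1) |
|---|---|
| 0.10 | 0.582 |
| 0.20 | 0.709 |
| 0.30 | 0.752 |

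Even with identical true rates, the two placebo columns would usually disagree.

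**The case for a change.** The strongest case for a change is that this is the primary endpoint, that the protocol is explicit, and that a SAP should not leave the reader to infer a grouping it spells out for secondary endpoints. A listing is not a tabulated proportion. With 6 per cohort, a one-participant gap between the placebo counts is 1/6 = 16.7 points. A reader who subtracted placebo from dose by eye, using the combined column, would be off by half of that, 8.3 points, in opposite directions for the two doses.

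The wording mismatch stands. The consequence mostly does not:

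- The SAP plans no AE difference or test, so the 8.3 points enter no specified output. They also presuppose a gap that chance alone produces 58% to 75% of the time at the assumed rates, and they vanish if the placebo rates match.
- Splitting placebo would not give a within-participant comparison. The columns would still be unpaired totals, and a combined column still contains each dose's own participants alongside the others. Paired information comes from the listings under either layout.
- Placebo infusion times differ only if 2 mg is chosen for Cohort 2, and nothing in the documents suggests that a longer saline infusion alters AE rates.

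**Conclusion.** No change to the plan is needed. SAP 12.1 is silent on one detail, whether the placebo column is shown by cohort. Silence does not establish that placebo will be pooled. The protocol supplies the rule, the SAP's own combined-cohort models supply the coding, and the shells are where the layout is settled. An analyst following both documents would produce the protocol's display.

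If a single placebo column were produced instead, the effect would be confined to one column of descriptive tables covering about 12 participants (an estimated 14 completers in the protocol synopsis). No alpha, power or sample size depends on it, and the cohort counts could be rebuilt from the listings. Each layout has a cost: one column blurs the cohort distinction, while two columns raise the zero-event upper limit from 26.5% to 45.9% and often display chance differences.

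This rests on the AE analysis remaining descriptive, as both documents plan it, and on the sequence-ordered listings being delivered. The numerical illustrations assume exactly 6 participants per cohort and AE rates of 10% to 30%, which the documents do not give.

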**3. OBJECTIVES AND ENDPOINTS**

Objectives	Endpoints
Primary	

 
To assess the safety and tolerability of a single dose of ERX-963 vs. placebo in patients with DM1
 
	
 
The proportion of participants with adverse events, serious adverse events (SAEs), and drug related adverse events
 

Secondary	

 
To assess the effect of intravenously-administered ERX-963 vs. placebo on sleepiness, vigilance, and working memory in patients with DM1
 
	Repeated measurements of the following: 
 
Stanford Sleepiness Scale (SSS) score
 
Psychomotor Vigilance Task (PVT) – No. of lapses and 1/Longest 10% Response time (1/RT) and median reaction time
 
One-back task – proportion of correct response
 
Clinical Global Impression – Improvement scale (CGI-I)
 
Patient Global Impression – Improvement scale (PGI-I)
 

Exploratory	

 
To correlate ERX-963 plasma concentrations to clinical efficacy endpoints in patients with DM1
 
To assess the effect of intravenously-administered ERX-963 vs. placebo on brain activity in patients with DM1
 
	Repeated measurements of the following: 
 
Plasma ERX-963 concentration
 
Stanford Sleepiness Scale (SSS) score
 
Psychomotor Vigilance Task (PVT) – No. of lapses and 1/Longest 10% Response time (1/RT) and median reaction time
 
One-back task – proportion of correct response
 
EEG – theta/alpha and theta/beta spectral ratios, and theta, alpha, and beta percentages
 

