#### **8.3.1. Time Period and Frequency for Collecting AE and SAE Information**

All SAEs will be collected from the signing of the informed consent form (ICF) until the End-of-Study visit or early discontinuations at the time points specified in the SoA ([Section 1.3](#)).

All AEs will be collected from the signing of the ICF until the End-of-Study visit or early discontinuations at the time points specified in the SoA ([Section 1.3](#)).

All SAEs will be recorded and reported to the sponsor or designee immediately and under no circumstance should this exceed 24 hours, as indicated in [Section 10.3, Appendix 3](#).

The investigator will submit any updated SAE data to the sponsor within 24 hours of it being available.

Investigators are not obligated to actively seek AE or SAE after conclusion of the study participation. However, if the investigator learns of any SAE, including a death, at any time after a participant has been discharged from the study, and he/she considers the event to be reasonably related to the study intervention or study participation, the investigator must promptly notify the sponsor.

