
 
• The investigator is obligated to assess the relationship (Related or Unrelated) between study intervention and each occurrence of each AE/SAE.
 
• A "reasonable possibility" of a relationship conveys that there are facts, evidence, and/or arguments to suggest a causal relationship, rather than a relationship cannot be ruled out.
 
• The investigator will use clinical judgment to determine the relationship.
 
• Alternative causes, such as underlying disease(s), concomitant therapy, and other risk factors, as well as the temporal relationship of the event to study intervention administration will be considered and investigated.
 
• The investigator will also consult the Investigator's Brochure (IB) and/or Product Information, for marketed products, in his/her assessment.
 
• For each AE/SAE, the investigator must document in the medical notes that he/she has reviewed the AE/SAE and has provided an assessment of causality.
 
• There may be situations in which an SAE has occurred and the investigator has minimal information to include in the initial report to sponsor/designee. However, it is very important that the investigator always make an assessment of causality for every event before the initial transmission of the SAE data to sponsor/designee.
 
• The investigator may change his/her opinion of causality in light of follow-up information and send a SAE follow-up report with the updated causality assessment.
 
• The causality assessment is one of the criteria used when determining regulatory reporting requirements.
 

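### SAP 12.1 counts adverse events only if they start by Study Day 2 of a period, so later non-fatal AEs and SAEs enter no all-AE or serious-AE proportion for the primary endpoint

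*SAP*

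**What the plan says.** **Protocol.** The primary endpoint (Section 3) is "The proportion of participants with adverse events, serious adverse events (SAEs), and drug related adverse events". Section 9.4.2 plans it as "Proportion of patients experiencing AEs, SAEs, drug-related AEs, adverse events resulting in discontinuation, by treatment and cohort". Neither place gives an onset window. Section 8.3.1 states: "All AEs will be collected from the signing of the ICF until the End-of-Study visit or early discontinuations", and it sets the same period for SAEs. Section 10.3.3 adds that "The investigator is obligated to assess the relationship (Related or Unrelated) between study intervention and each occurrence of each AE/SAE".

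**SAP 12.1.** The only definition of a TEAE is: "Treatment-emergent AEs will include AEs which start between the date and time of study drug dosing and through Study Day 2, within each period". Study Day is not defined. The overall summary table counts all TEAEs and then "all serious TEAEs, all drug-related TEAEs, number of deaths, and all severe TEAEs for the safety population". The frequency tables are for all TEAEs, and then, without the TEAE qualifier, "for all drug related adverse events, and for all adverse events resulting in discontinuation from study". On listings it says: "Subject listings of all TEAEs, serious TEAEs, and drug related TEAE will also be provided". The only other group named is pretreatment AEs, meaning events before the first dose.

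**SAP mockups.** The four visible AE tables, 14.3.1.1 to 14.3.1.4, are all titled as treatment-emergent tables, including the drug-related and discontinuation tables. The title of Listing 16.2.7.1 is not restricted. SAP 16 sends collected data that no table shows to subject listings.

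**The concern.** The SAP narrows the trial's only primary endpoint without saying so or giving a reason. An event that starts after Study Day 2 is neither pretreatment nor treatment-emergent, so it belongs to no group that the SAP tabulates. The planned all-AE and serious-AE proportions can therefore understate what the protocol defines.

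This matters most for a late event that the investigator rates as related. The rating is mandatory and would be on record, yet the event would be missing from the drug-related row of the overall summary. Other parts of the SAP do not close the gap:

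- SAP 10 plans no physical-examination summaries because significant findings go to the medical history or AE forms.
- SAP 12.2 summarizes hematology and chemistry at Screening and at the end of each treatment period, but not at End of Study.
- SAP 11 tabulates concomitant medications up to End of Study. A drug given for a late AE would be counted while the AE would not.

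**Working it through.** **1. Observation period.** The protocol gives about 57 days per participant in total. The maximum intervals reproduce it: 21 (screening) + 18 (washout) + 18 (follow-up) = 57. Each dose is thus followed by a gap of g = 4 to 18 days in which AEs are collected. The washout is counted from the Period 1 dosing day.

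**2. Where a late event is counted.** Take a non-fatal event that starts after Study Day 2 of a period.

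| Planned output | Is the event counted? |
|---|---|
| Overall summary: all, serious, drug-related and severe rows | No, all are TEAE rows |
| Overall summary: deaths | Row has no TEAE qualifier, but the event is non-fatal |
| Frequency table, all AEs | No, in both text and title |
| Frequency tables, drug-related and discontinuation AEs | Unclear: the text says all, the titles say treatment-emergent |
| Pretreatment AE listing | No |
| Listing 16.2.7.1 and the SAP 16 catch-all | Probably |

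SAP 12.1 describes no separate frequency table for SAEs. A late non-fatal SAE therefore has no proportion in which it is certain to appear.

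**3. Effect of one participant.** Inputs are at least 6 evaluable participants per cohort (Protocol 9.2, SAP 4.3) and an estimated 14 completers (protocol synopsis). I assume equal cohorts and no replaced participants. If a participant's only post-dose event is late, the proportion changes by 1/n:

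- ERX-963 column (B or C): 1/6 = 16.7 points; 1/7 = 14.3 points.
- Placebo as one group A across cohorts: 1/12 = 8.3 points; 1/14 = 7.1 points.
- Placebo split by cohort, as Protocol 9.4.2 asks: again 1/6 or 1/7.

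**4. Share of post-dose days outside the window.** The result depends on how Study Day is numbered:

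- Dosing is Day 1: (g − 2)/g. For g = 4, 2/4 = 50%. For g = 18, 16/18 = 89%.
- Dosing is Day 0: (g − 3)/g. For g = 4, 1/4 = 25%. For g = 18, 15/18 = 83%.

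These are shares of calendar days, not of events.

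**5. Pharmacological support for the window.** Protocol 4.2 gives a half-life of 40 to 80 minutes. With dosing as Day 1, the end of Day 2 is at least 24 h = 1440 min after dosing. That is at least 1440/80 = 18 half-lives, or 1440/40 = 36 with the shorter value.

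**The case against.** The strongest reply is that this is a choice of window length and not a breach of the protocol. Protocol 9.4 calls itself a summary and leaves detail to the SAP. Its AE definition requires a temporal association with the study intervention. Reporting by treatment needs some window, because events before the first dose cannot be assigned to a treatment. A drug that is gone within hours makes Day 2 a reasonable limit, and assigning an event up to 18 days after a dose to that dose would mix in background illness. Later events also stay visible: the AE listing has an unrestricted title, deaths carry no TEAE limit, SAP 5 tabulates discontinuation reasons, and 12 to 14 participants can be read line by line.

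Much of this stands. It supports keeping the Day 2 tables and limits the consequence. It does not remove the gap. The temporal-association wording sets no time limit, and the SAP gives none of the pharmacology as its reason. The endpoint is a proportion, which a listing does not supply. The field naming the treatment taken before the event is promised only for the TEAE listing; the layout of Listing 16.2.7.1 cannot be seen, so it may already carry that field for every event.

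A second limit is that the visible mockup contents are incomplete. AE tables end at page 52, listings begin at page 59, and the laboratory and vital-sign tables promised in SAP 12.2 and 12.3 are not among the visible titles. The table titles alone therefore cannot show that no other AE table exists. The conclusion rests on the text of SAP 12.1, which describes none. The April 2020 memo does not change the TEAE definition.

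**Conclusion.** The concern holds. Followed as written, SAP 12.1 leaves any non-fatal AE or SAE that starts after Study Day 2 of a period out of every all-AE and serious-AE proportion it specifies, although the primary endpoint has no such limit. For drug-related and discontinuation AEs the SAP contradicts itself, and the treatment of late events is unclear.

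One affected participant would mean 14 to 17 points in an ERX-963 column, or 7 to 8 points in a pooled placebo column, on the assumptions of equal cohorts and no replacements. How often this would occur is unknown. The calendar-day shares show how much follow-up lies outside the window, not how much risk.

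This should be fixed but is not critical: the sample is small enough to read in full, and no hypothesis test is specified for this endpoint.

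**What to change.** - Keep the Day 2 tables as the acute view and state why that window was chosen.
- Add the same tables for all AEs, SAEs, drug-related AEs and AEs leading to discontinuation, with onset from each dose to the next dose or End of Study. Assign each event to the last treatment received, and show results by treatment and cohort as in Protocol 9.4.2.
- Make sure the field for the preceding treatment covers later events in the listing.
- Define Study Day, reconcile the titles of Tables 14.3.1.3 and 14.3.1.4 with the text of SAP 12.1, and state how deaths are counted.

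The cost is SAP wording, one more run of four tables already mocked up, and at most one extra listing field. No new data are needed. The drawback is that follow-up in the added tables varies from 4 to 18 days per period, which is why the acute tables should stay beside them.
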